6.1.4 Labelling and Packaging

The IMP will be clearly labelled for clinical trial use only. The participant's study ID number will be displayed on the treatment pack.

Each pack will be labelled in accordance with Annex 13 of Volume 4 of The Rules Governing Medicinal Products in the EU: Good Manufacturing Practices, with the primary and secondary packaging remain together throughout the trial.

Detailed prescribing and administration instructions will be provided with the treatment pack. Dose initiation in first 2-4 weeks will be guided by a regular phone calls and instructions.

6.1.5 Storage

The trial drugs will be stored in participating hospital pharmacies as per requirements for the branded products. They will be stored in a restricted access area where temperature is monitored and maintained below 25°C. Stability data exist which demonstrates that cilostazol is stable for 3 years without temperature restrictions. ISMN is stable for 3 years at temperatures below 25°C.

6.2 DOSING REGIME

Patients will be supplied with trial drug in its usual (marketing) packaging unaltered. Patients will be issued with instructions reflecting the allocated dosing schedule which will instruct them what tablets they have to take initially and how to increase the dose. They will receive a phone call after 1 to 2 and 3 to 4 weeks as per schedule below to guide dose escalation. If a patient encounters intolerable side effects they will be asked to return to the highest previously tolerated dose and this will be recorded in the eCRF and hospital notes. They will be given clear instructions by phone or in person (depending on the stage of the trial). Patients will also receive instruction on how they should decrease the dose of trial drug incrementally at the end of the study.

Table 1: Patients randomised to Isosorbide Mononitrate alone - either XL or non-XL preparations, example

If a slow release preparation is not available, then a non-slow release preparation may be used, but the dose should be given half in the morning (eg 08.00 am) and half in the evening (eg 18.00hrs)

ISMN XL Dosing Regime			ISMN non-XL Dosing Regime		
Day	ISMN XL 25mg		Day	ISMN non-XL 20mg	
	Morning	Evening		Morning	Evening
1-5	25mg	nil	1-5	nil	20mg
6-10	50mg	nil	6-10	20mg	20mg
11-15	50mg	nil	11-15	20mg	20mg
16-20	50mg	nil	16-20	20mg	20mg
At end of study			At end of study		
Week	Morning	Evening	Week	Morning	Evening
53	25mg	Nil	53	20mg	Nil
54	Nil	Nil	54	Nil	Nil

Table 2: Patients randomised to cilostazol alone

Cilostazol Dosing Regime		
Day	Cilostazol	
	Morning	Evening
1-5	Nil	50mg
6-10	50mg	50mg
11-15	50mg	100mg
16-20	100mg	100mg
At end of study		
Week	Morning	Evening
53	50mg	50mg
54	Nil	Nil

Table 3: Patients randomised to both Isosorbide Mononitrate and Cilostazol

ISMN XL/Cilostazol Dosing Regime				
Day	Isosorbide Mononitrate XL 25mg		Cilostazol	
	Morning	Evening	Morning	Evening
1-5	25mg	nil	Nil	Nil
6-10	50mg	nil	Nil	Nil
11-15	50mg	nil	Nil	50mg
16- 20	50mg	nil	50mg	50mg
21-25	50mg	nil	50mg	100mg
26-30	50mg	nil	100mg	100mg
At end of study				
Week	Morning	Evening	Morning	Evening
53	25mg	Nil	50mg	50mg
54	Nil	Nil	Nil	Nil

ISMN non-XL/Cilostazol Dosing Regime				
Day	Isosorbide Mononitrate 20mg		Cilostazol	
	Morning	Evening	Morning	Evening
1-5	nil	20mg	Nil	Nil
6-10	20mg	20mg	Nil	Nil
11-15	20mg	20mg	Nil	50mg
16- 20	20mg	20mg	50mg	50mg
21-25	20mg	20mg	50mg	100mg
26-30	20mg	20mg	100mg	100mg
At end of study				
Week	Morning	Evening	Morning	Evening
53	20mg	Nil	50mg	50mg
54	Nil	Nil	Nil	Nil

Table 4: Patients randomised to neither Isosorbide Mononitrate or Cilostazol

Neither ISMN/Cilostazol Dosing Regime				
Day	Isosorbide Mononitrate		Cilostazol	
	Morning	Evening	Morning	Evening
1-4	Nil	Nil	Nil	Nil
5-8	Nil	Nil	Nil	Nil
9-12	Nil	Nil	Nil	Nil
13, 14	Nil	Nil	Nil	Nil
At end of study				
Week	Morning	Evening	Morning	Evening
53	Nil	Nil	Nil	Nil
54	Nil	Nil	Nil	Nil

6.3 DOSE CHANGES

Doses will be initiated as per the example regime in section 6.2. Patients will be allowed to increment the dose more slowly, or to stay at a previously tolerated dose where their symptoms preclude reaching the target dose stated in 6.2. Variation of dose like this will not count as a protocol deviation. Patients will be able to stay on the dose they can tolerate. If necessary, this will be done under close guidance of the researcher. There will be no other changes to the doses described in section 6.2.

6.4 PARTICIPANT COMPLIANCE

Adherence and the tolerability of these treatments is a key outcome measure as part of the trial feasibility assessment. Symptoms related to taking either drug will be assessed using a structured questionnaire given as per schedule and the patient will be asked if they are continuing to take the medication at each review of symptoms.

As indicated in 7.1 below, during the start-up phase, patients will be asked to contact the local PI or delegated research nurse if they experience adverse symptoms, or trial help line should neither of the above be available. Once patients are established on their steady dose of tablets, they will be asked to inform the trial team via the help line or contact their local PI if they experience untoward symptoms (in addition to contacting their GP or other relevant hospital service). Such episodes of contact will be recorded in the eCRF or AE form or reported as SAEs as appropriate.

Patients will be asked to return any unused tablets to the hospital pharmacy that provided the tablets at six and 12 months. Pharmacy will submit a tablet count to the eCRF.

6.5 OVERDOSE

Cilostazol: The SPC for Cilostazol states that there is limited information on the effects of acute overdose in humans. It is anticipated to feature severe headache, diarrhoea, tachycardia and possibly cardiac arrhythmia. Management would be supportive care and gastric lavage as appropriate.

Isosorbide Mononitrate: The SPC describes the expected effects of isosorbide mononitrate in overdose and details measures for management.

The risk of overdose will be minimised by excluding patients with a history of overdose or suicide, or significant active mental health problems.

6.6 OTHER MEDICATIONS

6.6.1 Non-Investigational Medicinal Products

Not applicable

6.6.2 Permitted Medications

Patients may continue to take all usual prescribed medication during the study except those listed in 6.6.3 and in the exclusion criteria.

6.6.3 Prohibited Medications

Isosorbide mononitrate:

Phosphodiesterase 5' inhibitors (tadalafil, sildenafil, vardenafil).

Cilostazol:

Other strong inhibitors of metabolic enzymes CYP3A4 or CYP2C19 (e.g. diltiazem).

Erythromycin, clarithromycin, ketoconazole, itraconazole, omeprazole

Dual antiplatelet drugs (e.g. aspirin and clopidogrel simultaneously)

Anticoagulants (warfarin, heparin, dabigatran, rivaroxaban, apixaban)

Although not noted in the BNF, SPCs for cilostazol indicate caution is advised with other strong inhibitors of metabolic enzymes CYP3A4 or CYP2C19, such as simvastatin, atorvastatin, lovastatin, carbamazepine, phenytoin, rifampicin. BNF notes caution with isosorbide mononitrate and hypotensive agents such as diltiazem, hydralazine, etc.

Please refer to the SPCs for full details.

7 STUDY ASSESSMENTS

7.1 SAFETY ASSESSMENTS

Patients will be encouraged to contact the Trial team if, after randomisation, they have any concerns at all about the study drugs, their stroke, if they develop symptoms suggestive of a recurrent vascular event, if they become cognitively impaired or have another medical problem.

Patients will be assessed at 1-2-weekly intervals in the first month and six monthly intervals as per Study Flow diagram and Section 7.2 for the presence of any symptoms related to taking the trial drugs. This will include a structured questionnaire to assess for headache, dizziness, palpitations, bleeding, recurrent neurological or cardiac symptoms as outcome events that are also common after stroke, and adherence to medication.

7.2 STUDY ASSESSMENTS

Study assessments are shown in **Table 5** below, and in **Figure 2**.

Table 5: Study Assessments

Assessment	Prior to Baseline	Visit 1 Baseline	Week 1-2 FU	Week 3-4 FU	6 month FU	12 month FU
Screening for eligibility and Consent ¹ ;	X^s					
Confirm and document ongoing consent		X^s				
Medical including drug history		X^s				
Assess MR or CT diagnostic scan and send a copy to Edinburgh		X^s				
Randomisation		X^s				
Haematology (full blood count) and Biochemistry (urea, electrolytes, creatinine) – most recent value obtained since time of index stroke is acceptable unless clinical reason to expect change		X^s				
Blood Pressure recorded		X^s				X^{s,*}
Cognitive test: document years of education; Montreal Cognitive Assessment (MOCA)		X^s				
Timed Trail Making Test B		X^s				X^{s,*}
Dispense trial medication ²		X^s			X^s	
Structured questionnaire: symptoms; medication history and IMP tablet adherence			X^s	X^s	X^c	X^c
Structured Q: recurrent vascular events, mRS, TICS, TMOCA, SIS, ZUNG					X^c	X^c
Obtain IQCODE (post/phone) from relative						X^c
Follow-up brain MRI						X^s
Health Economics data: EQ-5D-5L, EQ-VAS						X^c
Adverse event / con meds reporting as necessary			X^s	X^s	X^{s,c}	X^{s,c}

¹Consent will be obtained before the data collection procedures commence or randomisation is performed.

Randomisation occurs at the end of the baseline visit. ^{*}at 12 months in some centres only. ²Dispensing in 3-monthly intervals is allowed. ^sAssessment performed by local site team. ^cAssessment performed by blinded assessor who is part of the central trial team.

SIS=Stroke Impact Scale, TICS= Telephone Interview for Cognitive Status, TMOCA= telephone MOCA.

Medical history: Will be performed by the study researcher and will include details of incident stroke, past medical history, vascular risk factors, medication history and years of education.

Baseline brain MR (preferred wherever possible) or CT: To identify the index stroke or exclude other causes of symptoms, and assess the burden of SVD – this is the clinical scan with T2, FLAIR, T1, T2* and diffusion imaging or CT obtained soon after the presentation with stroke that shows either:

- a recent, relevant (in time and location) acute lacunar infarct,
- or, if no visible acute lacunar infarct, there is no competing pathology as a cause for stroke (e.g. no acute cortical infarct, no acute lacunar or cortical intra-cerebral haemorrhage, no stroke mimic such as tumour, subdural haematoma). Scans will be sent for central reading.

Cognitive baseline testing: Patients will be assessed at baseline using the Montreal Cognitive Assessment (MoCA), the timed Trail Making Test B for processing speed/executive function, and ZUNG for mood. Their years in full time education will be recorded.

Symptoms and adverse effects: Will be assessed using a structured validated questionnaire to assess for recurrent neurological symptoms and whether these meet clinical criteria for TIA or stroke, angina or MI, peripheral vascular disease (and details thereof), headache, dizziness,

palpitations, altered bowel habit, and adherence to medication, and if any other symptoms have occurred. The patient will be asked whether were severe enough to interfere with normal daily activities. Patients will also be able to report any other symptoms and describe them in detail. Depending on the time point in the study this will either be completed face to face at a study visit or by telephone.

Tablet adherence: Will be assessed by asking the patient about their medication usage and recording the details in the eCRF. In addition, patients will be asked to return any packs of unused tablets to the hospital pharmacy at the end of the trial. All returned tablets will be counted at Pharmacy and then be destroyed.

Blood pressure: Will be assessed using a validated clinical instrument that meets British Hypertension Society standards.

Haematology and biochemistry: Full blood count, urea and electrolytes and renal function will be obtained from the most recent sample obtained since the time of the index stroke. If there is a clinical reason to expect change in which case the full blood count and biochemistry should be repeated prior to randomisation. These samples will be analysed in the hospital haematology or biochemistry labs in the centre in which the patient has been recruited.

Neurological outcomes: Information on recurrent stroke, TIA, angina, MI, PVD will be assessed by postal or phone questionnaire at 6 and 12 months. Patients will be encouraged to seek medical advice if they develop new neurological events during the trial.

Functional outcome: modified Rankin Scale to assess dependency at 6 and 12 months. If participants are unable to be contacted, the central assessor will obtain the most recent modified Rankin Score from the local staff (if available).

Cognitive outcomes: Telephone MOCA, Telephone Interview for Cognitive Status (TICS), mobility and physical functioning sections of the Stroke Impact Scale and the ZUNG will be collected remotely at six and 12 months by the central trial team. TRAILS B will be repeated when attending for 1 year MR in Centres that are able to do this. TICS will be collected for consistency with prior and ongoing trials (ENOS, TARDIS, RIGHT 2, TICH) and good comparability.⁶² TMOCA will be collected for comparison with TICS for potential use in future trials as it purports to assess executive function more than TICS. IQCODE will be collected from the relative/partner/carer by post or phone.

Health economics: EQ-5D-5L, EQ-VAS, return to work, hospitalisation, need for long term supportive care will be collected at 12 months.

Follow-up Brain MRI: all patients will have repeat brain MRI at 12 months to assess burden of WMH, microbleeds, lacunes, new infarcts or haemorrhage and atrophy and where feasible to assess diffusion tensor tissue parameters. These scans will be sent to Edinburgh for central blinded adjudication.

Follow-up at 6 and 12 months will be by post and telephone, blinded to allocated treatment. A trained assessor who is part of the central trial team and based either at the University of Edinburgh or University of Nottingham and who is blinded to treatment and baseline clinical information, will first confirm with the GP that the participant is contactable. They will then contact the patient or carer by post and phone to administer the questionnaires following a standardised script.

In addition to the assessments detailed above, participants will receive one to five informal contacts over the duration of their trial participation. One will consist of a participant newsletter and any other informal contacts will be a brief phone call or additional participant newsletter. During those contacts, a member of the central or site teams will update participants on the trial status, thank them for their continued help with the study, and give them an opportunity to ask questions.

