4.2 INCLUSION CRITERIA

- Clinical lacunar stroke syndrome.
- Brain scanning* with MR including diffusion imaging wherever possible, and obtained soon after the presentation with stroke, shows either:
 - a recent, relevant (in time and location) acute lacunar infarct on diffusion MR imaging¹,
 - or, if no visible acute lacunar infarct on diffusion MR imaging² then there is no competing pathology as a cause for stroke (e.g. no acute cortical infarct, no acute intra-cerebral haemorrhage, no stroke mimic such as tumour, subdural haematoma);
 - or, if only a CT brain scan is available² as in section 3 above, then there is a small relevant (in age and location) subcortical infarct, or if no infarct then there is no competing pathology as a cause for stroke (e.g. no acute cortical infarct, no acute intra-cerebral haemorrhage, no stroke mimic such as tumour, subdural haematoma).

¹Note that if there is no acute lacunar infarct on MR diffusion imaging but there is a recent-appearing lacunar infarct on FLAIR, T2, or T1 (i.e. no cavitation or ex-vacuo effect; may be slightly swollen, ill-defined edges; or scan in the few weeks before the stroke does not show a lesion but there is an acute lacunar infarct on MR T2, FLAIR, T1 scanning after the stroke in an appropriate area of the brain for symptoms), then the T2, FLAIR, T1 lesion may be counted as the acute lacunar infarct in the absence of a diffusion lesion. Similarly, on CT² a recent relevant small subcortical infarct would not show cavitation or shrinkage/ex vacuo effect.

²Note that about a third of patients with a clinically definite lacunar syndrome do not have a corresponding recent infarct visible on MRI but should still be classed as 'lacunar stroke' if no other explanation can be found for the symptoms. The presence of a recent cortical infarct on FLAIR, T2, T1, the recent timing being indicated by the characteristics above, would count as a competing pathology.

Note that the complete absence of any abnormality on MR or CT brain imaging (no acute subcortical infarct or pre-existing SVD such as white matter hyperintensities, lacunes, etc.) while occasionally seen in lacunar stroke is unusual and should question the diagnosis of lacunar ischaemic stroke.

- Age > 30 years
- Independent in activities of daily living (modified Rankin ≤ 2)
- Capacity to give consent themselves

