4.3 EXCLUSION CRITERIA

4.3.1 General exclusion criteria

- Other significant active neurological illness present since suffering stroke (e.g. recurrent seizures, multiple sclerosis, brain tumour). Well-controlled epilepsy present prior to the stroke, a single seizure at onset of the stroke or provoked seizure is not an exclusion.
- Requiring assistance with activities of daily living (Modified Rankin ≥ 3)
- Has been diagnosed as having dementia on formal clinical assessment
- Diagnosis of hypotension, defined as sitting systolic blood pressure less than 100mmHg
- Unable to swallow tablets
- Planned surgery during the trial period including carotid endarterectomy. Note prior and apparently successful carotid endarterectomy (or other surgery) is not an exclusion criterion and patients who would otherwise be eligible but require endarterectomy first may be randomised after recovery from successful endarterectomy.
- Other concurrent life threatening illness
- Unlikely to be available for follow-up (e.g. moving outside or visitor to the area)
- History of drug overdose or attempted suicide or significant active mental illness
- Pregnant or breastfeeding women, women of childbearing age not taking contraception. Acceptable contraception in women of childbearing age is a “highly effective” contraceptive measure as defined by the Clinical Trials Facilitation Group (http://www.hma.eu/fileadmin/dateien/Human_Medicines/01-About_HMA/Working_Groups/CTFG/2014_09_HMA_CTFG_Contraception.pdf) and includes combined (oestrogen and progesterone containing) or progesterone-only contraception associated with inhibition of ovulation, or intrauterine device or bilateral tubal occlusion. Contraception must be continued for up to 30 days after the end of the IMP dosing schedule.
- Renal impairment (creatinine clearance <25 ml/min)
- Hepatic impairment
- Current enrolment in another Clinical Trial of Investigational Medicinal Product (CTIMP); still in extended follow-up beyond the CTIMP primary outcome and no longer taking that trial's IMP is not an exclusion to enrolment in LACI-2.
- Unable to tolerate MRI or contraindication to MRI (Claustrophobia, Pacemaker)

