Participants with an indication for or contraindication to one of the trial drugs may still be randomised to the other trial drug. If a participant allocated to both trial drugs develops a contraindication to one of the trial drugs after randomisation into the trial, then they should discontinue that drug but continue to take the other trial drug. If a patient has to discontinue either or both drugs, they should continue to be followed up in the trial as planned (unless they withdraw from the trial). Patients should remain in follow up until the end of the trial follow up period, even if they discontinue trial drug, unless they withdraw from the trial.

The study will be performed open label. Placebo tablets are not available and masking by encapsulation is too complicated and expensive. However, blinding of outcomes is important to obtain unbiased information about tolerability, safety and efficacy. As such, structured symptom questionnaires, ascertainment of clinical outcomes and MRI analysis will be collected by individuals blinded to treatment allocation.

Treatment Allocation: Participants randomised to start drug will be provided with their allocated drug/s after randomisation at the baseline visit, which they will start on the next day (i.e. day 1, week 1). In the event that there is any delay between receiving the trial tablets and starting the treatment, then the patient will receive a reminder telephone call shortly before the day that the medication should be commenced. The first day of treatment defines day 1, week 1.

Participants will be supplied with trial tablets from the hospital pharmacy to cover a maximum period of six months. Detailed dated instructions on dosing will be provided in the patient pack. The participant will be telephoned between the end of weeks 1 and 2 and between the end of weeks 3 and 4, and other times during drug introduction as necessary, as well as follow-up time points, to ensure they are taking the medication correctly.

Drugs will be provided in their packs as marketed and licensed (i.e unaltered) and dispensed by the participating hospital pharmacy under research protocols.

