Haematology (full blood count) and Biochemistry (urea, electrolytes, creatinine) – most recent value obtained since time of index stroke is acceptable unless clinical reason to expect change		X ^s				
Blood pressure		X ^s				X ^s [‡]
Cognitive test: document years of education; Montreal Cognitive Assessment (MOCA)		X ^s				
Timed Trail Making Test B		X ^s				X ^s [‡]
Dispense trial medication ²		X ^s			X ^s	
Structured questionnaire: symptoms; medication history and IMP tablet adherence			X ^s	X ^s	X ^c	X ^c
Structured questionnaire: recurrent vascular events, mRS, TICS, t-MOCA, SIS, ZUNG					X ^c	X ^c
Obtain IQCODE (post/phone) from relative						X ^c
Follow-up brain MRI						X ^s
Health Economics data: EQ-5D-5L, EQ-VAS						X ^c
Adverse event / con meds reporting as necessary			X ^s	X ^s	X ^{s,c}	X ^{s,c}

[†] Consent will be obtained before the data collection procedures commence or randomisation is performed. Randomisation occurs at the end of the baseline visit.

[‡] at 12 months in some centres only.

² Dispensing in 3-monthly intervals is allowed.

^s Assessment performed by local site team.

^c Assessment performed by blinded assessor who is part of the central trial team.

SIS: Stroke Impact Scale; TICS: telephone interview for cognitive status; t-MOCA: telephone MOCA.

SECTION 4. STATISTICAL PRINCIPLES

Confidence and p values**16 Level of statistical significance**

The results of analyses and comparisons will be shown with $p < 0.05$.

17 Multiplicity

No adjustment will be made for multiplicity.

18 Levels of confidence intervals

The results of analyses and comparisons will be shown with 95% confidence intervals.

19 Adherence

19a Definition: 75% of patients will be able to tolerate trial medication, in at least half dose, up to one year after randomisation (i.e. less than 25% will stop trial medication completely through inability to tolerate the drugs).

19b Adherence presentation: See Table 4.

19c Protocol deviations: Protocol violations will be reported to the sponsor within 24 hours of becoming aware of the violation. Protocol deviations will be recorded in a protocol deviation log with these submitted to the sponsors every 3 months.

19d Protocol deviation presentation: Listing of violations and deviations and their frequency.

20 Analysis populations

Three populations are defined:

1. Intention-to-treat: All consented participants with a primary outcome measure.

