2. Per protocol: All consented participants with a primary outcome measure who received at least one dose of randomised medication and who had no protocol violation, e.g. they fulfilled all eligibility criteria.
3. Safety: All consented participants who received at least one dose of randomised medication.

Multiple variable analyses will include all patients with complete data for the dependent and each independent variable. All available data will be used, and missing data will not be imputed.

SECTION 5. TRIAL POPULATION**21 Screening data**

No screening logs will be kept so that data collection can be prioritised.

22 Eligibility

1. Clinical lacunar stroke syndrome.
2. Brain scanning with MR including diffusion imaging wherever possible, and obtained soon after the presentation with stroke, which showed either:
 - a. A recent, relevant (in time and location) acute small subcortical (i.e. lacunar) infarct on diffusion MR imaging.
 - b. If no visible acute small subcortical infarct on diffusion MR imaging then there is no competing pathology as a cause for stroke (e.g. no acute cortical infarct, no acute intra-cerebral haemorrhage, no stroke mimic such as tumour, subdural haematoma);
 - c. If only a CT brain scan is available, then there is a small relevant (in time and location) subcortical (i.e. acute lacunar) infarct, or if no infarct then there is no competing pathology as a cause for stroke (e.g. no acute cortical infarct, no acute intra-cerebral haemorrhage, no stroke mimic such as tumour, subdural haematoma).

3. Age >30 years.
4. Independent in activities of daily living (modified Rankin Scale <=2).
5. Capacity to give consent themselves.

23 Recruitment

Recruitment will be summarised in a CONSORT flow diagram.

24 Withdrawal/follow-up

Withdrawals, and missed follow-ups and their timing will be summarised in the CONSORT flow diagram.

25 Baseline patient characteristics

25a Baseline characteristics: These will comprise demographic, education, premorbid function, cognitive ability, medical history, blood pressure, stroke investigations, clinical and brain imaging parameters (Table 1).

25b Summarisation: Data will be shown as number (%), median [interquartile range] or mean (standard deviation) as appropriate.

SECTION 6. ANALYSIS

26 Outcome definitions

26a Specifications:

Primary endpoint

Feasibility of a Phase III efficacy trial assessed as:

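### Protocol 7.2 allows an undated, possibly pre-randomisation and unblinded site mRS to stand in for the 6- or 12-month score when a participant cannot be contacted

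*Protocol*

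**What the plan says.** Protocol 7.2 sets the outcome: "Functional outcome: modified Rankin Scale to assess dependency at 6 and 12 months". The next sentence gives the fallback for both time points: "If participants are unable to be contacted, the central assessor will obtain the most recent modified Rankin Score from the local staff (if available". It states no time window, no earliest date and no blinding condition.

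Table 5 of the protocol lists follow-up mRS in one row, "Structured Q: recurrent vascular events, mRS, TICS, TMOCA, SIS, ZUNG", marked at 6 and 12 months only, both times for the central team. SAP Table C repeats this, and its footnote to those entries reads "Assessment performed by blinded assessor who is part of the central trial team".

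Entry is restricted on the same scale. Protocol 4.2 requires "Independent in activities of daily living (modified Rankin ≤ 2" and 4.3.1 excludes "Requiring assistance with activities of daily living (Modified Rankin ≥ 3". SAP Tables 2 and 3 define dependency as an mRS above 2.

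On blinding, Protocol 5.5.1 describes an open-label trial in which "ascertainment of clinical outcomes and MRI analysis will be collected by individuals blinded to treatment allocation". On missing data, SAP section 20 says "All available data will be used, and missing data will not be imputed", and section 28 prefers whichever approach uses the most available data. SAP 4c gives the SAP precedence over the protocol. No part of the SAP refers to the site-held mRS.

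**The concern.** No follow-up mRS is scheduled at sites, so the score a site is certain to hold is the one taken at entry. Measured against a threshold of mRS above 2, that score is always a non-event. If it is accepted as a follow-up value, any error runs one way, towards independence. SAP section 28 itself says that failure to complete assessment after stroke is often linked to cognition or deficit, so the people affected may be more dependent than average.

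A later site score avoids that problem but comes from staff who know the allocation, in a trial whose protection against bias is a blinded end-point.

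The mRS feeds the dependency component of the composite, the ordinal mRS analysis, both cognition scales in SAP Table E and the global outcome in SAP section 29. Estimating event rates for Phase III is a stated purpose of the trial. Baseline mRS is also an adjustment covariate (SAP Table 3), so covariate and outcome could be the same measurement.

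The protocol does bound a comparable rule: for blood tests, the latest value must post-date the index stroke. The mRS rule has no such limit.

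**Working it through.** **Inputs from the documents.** Expected dependency 15% (Protocol Table 6). Composite model D: 45% control, 36% active, 80% power, alpha 5%, 1:1, Fleiss correction, 976 before and 1100 after 10% losses (Protocol 9.1, Table 7). Retention target above 95% (SAP 26a). Randomised: 363 (SAP Table 2).

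**Assumptions, not in the documents.** u is the share of participants whose entry mRS is carried forward: 5% (the edge of the retention target) or 10% (the Phase III loss assumption). r is their true dependency: 15%, 30% or 45%. Dependency among those contacted is 15%.

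**Step 1: reproduce the plan's figure.** Two-proportion formula for 45% against 36%, two-sided 5%, 80% power: 932 in total without continuity correction, 976 with it, which matches the plan exactly. Then 976 / 0.90 = 1085, close to the stated 1100.

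**Step 2: effect on recorded dependency, upper bound.** True rate = (1 − u) × 15% + u × r. Recorded rate = (1 − u) × 15%. Shortfall = u × r.

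| u | r | True | Recorded | Shortfall (points) | Per 400 |
|---|---|---|---|---|---|
| 5% | 15% | 15.00% | 14.25% | 0.75 | 3 |
| 5% | 30% | 15.75% | 14.25% | 1.50 | 6 |
| 5% | 45% | 16.50% | 14.25% | 2.25 | 9 |
| 10% | 15% | 15.00% | 13.50% | 1.50 | 6 |
| 10% | 30% | 16.50% | 13.50% | 3.00 | 12 |
| 10% | 45% | 18.00% | 13.50% | 4.50 | 18 |

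**Step 3: what treating these scores as missing would recover.** The observed rate becomes 15%. The shortfall is then 0 to 1.5 points at u = 5% and 0 to 3 points at u = 10%. Barring the entry score removes u × 15%, that is 0.75 or 1.5 points. The rest is ordinary informative missingness, which no wording of the fallback can remove.

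**Step 4: carry-through to model D, upper bound.** Suppose no misclassified participant has another composite event, and keep the 20% relative reduction. At u = 5% and r = 15% to 30%, the composite falls from 45% to 44.25% to 43.5%, and the total before losses rises from 976 to 1004 to 1032. At u = 10% it falls to 43.5% to 42.0%, and the total is 1032 to 1092. In the most extreme cell above, 45% − 4.5 = 40.5%, still inside the plan's 40-50% criterion.

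**Step 5: unequal use between arms, illustration.** Assume true dependency of 15% in both arms, with the entry score used for 2% of controls and 8% of active participants. Recorded rates are 14.7% against 13.8% (ratio 0.94) for r = 15%, and 14.4% against 12.6% (ratio 0.88) for r = 30%: an apparent benefit without a true effect.

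**Step 6: retention.** 0.95 × 363 = 344.85, so the target needs 345 participants. If 10% (36) were uncontactable, 327 would remain, and counting 18 of the 36 as followed up would reach 345. This matters only if such participants are counted as retained, on which the documents are silent.

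**The case against.** A reader might infer that hard-to-reach participants are automatically recorded as independent. The documents do not support that.

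- The rule asks for the latest score, and only where one exists. The entry mRS exists for everyone, so a request limited in that way reads more naturally as meaning a later score. If the site has none, the value stays missing. The text also does not say that the site's score becomes the analysed value.
- Protocol 7.2 keeps the central assessor unaware of baseline clinical information, and supplying the entry score would breach that.
- Sites do see participants later. Protocol section 3 describes visits for prescriptions and the 12-month MRI, and follow-up by site or central staff. An unscheduled site mRS is plausible.
- Safeguards come first. The assessor checks with the GP and contacts the patient or carer (7.2), and an informant is sought partly in case of incapacity (5.2). SAP section 28 allows record linkage.

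All of this stands, and it limits how often an entry score could be used. It does not close the gap. No mRS is scheduled at those site visits, and participants allocated to neither drug have nothing to collect, so later site scores might be commoner in the drug arms (an inference, not a stated fact).

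Two other strong readings also fail. One is that the fallback breaches the SAP's rule against imputation. A score obtained from another source is not statistical imputation; equally, it would not look missing, so that rule need not catch it. The other is that lost participants are counted as retained. Nothing defines retention by having an mRS, and SAP section 24 reports missed follow-ups in the CONSORT diagram.

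**Conclusion.** The concern holds as a permissive gap. Neither document stops an entry score, necessarily 2 or less, from standing as a 6- or 12-month outcome, and any later site score would be from open-label staff. The direction of error from an entry score is certain; its frequency is unknown.

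The shortfall in recorded dependency is at most 0.75 to 2.25 points at 5% uncontactable and 1.5 to 4.5 points at 10%, given the assumed 15% to 45% true dependency and the entry score being used for every uncontacted participant. If the retention target is met, the lower range is the relevant one. The effect falls on a component of a secondary composite, not on the primary feasibility endpoint, unless fallback scores are allowed to count towards retention. This is a cheap improvement and not an essential correction.

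**What to change.** In Protocol 7.2 and SAP section 28:

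- Accept a site mRS only if it is dated and post-dates randomisation. Never use the entry score. Otherwise treat the mRS as missing.
- Record the date and source of each score (central blinded or site), and report use of the fallback by arm.
- Add a sensitivity analysis of the mRS and the composite using central blinded scores only.
- State that a fallback mRS alone does not count a participant as retained at one year.

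A fixed window around the follow-up date is a trade-off that I would not impose: it could discard a genuine later score showing dependency. With the date recorded, readers can judge how close each score is.

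The cost is a few sentences and fields for date and source in the eCRF, a few more missing mRS values and possibly a slightly lower retention figure.
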